## Lay Summary

Transgender women (TW) are at the highest risk for exposure to interpersonal violence even compared to other sexual and gender minority individuals. Empowerment Self-Defense (ESD) training, a specific violence prevention approach that teaches participants strategies for actively resisting assault, holds tremendous promise for reducing risk of violent victimization. Indeed, research consistently shows that assertive and physical forms of resistance are effective in deterring rape. Moreover, in randomized controlled trials, ESD violence prevention training has been shown to reduce rates of victimization among college students by nearly half at 1-year follow-up. Unfortunately, diverse TW are rarely included in ESD violence prevention research and programming. This exclusion is problematic not only because TW comprise the highest need population for targeted violence prevention, but also because theoretical models of gender identity stigma hold that social and psychological stressors specific to gender-minority identity increase risk for interpersonal violence along multiple unique pathways. Standard ESD violence prevention programs do not incorporate content, materials, or strategies tailored to the specific pathways by which TW are impacted by interpersonal violence. This study fills this substantial gap in prevention science by developing an ESD violence prevention training specifically tailored to TW. The proposed project aims to develop and refine a tailored ESD violence prevention training for diverse TW through a series of sequential Aims: a) develop an initial draft of an ESD violence prevention curriculum tailored to TW (Aim 1); b) evaluate the feasibility and acceptability of recruitment, assessment procedures, retention and follow-up procedures, and implementation of the new intervention (Aim 2); and c) assess the preliminary efficacy of the tailored intervention program to increase use of self-protective resistance strategies, mitigate minority stressors and attitudinal barriers to self-defense, and reduce rates of exposure to violence (Exploratory Aim). We will accomplish these aims using a two-phase research design that begins with formative gualitative work engaging research partners on a community board and a small sample of research participants. Information for Phase 1 can be located in Protocol number 2020-0017. Further refinement and assessment of the feasibility and acceptability of the curriculum using Phase 1 findings will occur in Phase 2 through the delivery of the tailored ESD curriculum to 3 groups of 16 TW. To assess the preliminary efficacy of the tailored intervention, program participants will complete a battery of validated guestionnaires assessing use of resistance strategies, gender-minority and general psychological factors hypothesized to mediate the behavioral effects of the intervention, and exposure to victimization experiences prior to, immediately following, and 6 months

post-completion of the training. Together, the proposed research will lay the foundation for a large-scale randomized controlled trial (RCT) of the tailored ESD violence prevention curriculum.

Do you have a scientific protocol or No a sponsors protocol?

Page 2 of 36

2021-0291

**Initial Application** 

**[name]** 

## 3. Other Personnel

None

Page 4 of 36

2021-0291

**Initial Application** 

**[name]** 

## 5. Research Design - Overview

## **Research Purpose and Hypothesis**

This study leverages the strong evidence-base for Empowerment Self-Defense (ESD) violence prevention to address disparities in violence exposure among TW. The overarching goal of this R21 is to develop and refine a tailored ESD violence prevention training for diverse TW through a series of sequential Aims: a) develop an initial draft of an ESD violence prevention curriculum tailored to TW (Aim 1) (See protocol number 2020-0017); b) evaluate the feasibility and acceptability of recruitment, assessment procedures, retention and follow-up procedures, and implementation of the new intervention (Aim 2); and c) assess the preliminary efficacy of the tailored intervention program to increase use of self-protective resistance strategies, mitigate minority stressors and attitudinal barriers to self-defense, and reduce rates of exposure to violence (Exploratory Aim). Together, the proposed research will lay the foundation for a large-scale randomized controlled trial (RCT) of the tailored ESD violence prevention curriculum. We will accomplish these aims using a two-phase research design that begins with formative qualitative work engaging research partners on a community board and a small sample of research participants (See protocol number 2020-0017). This data will be used to inform the development and refinement of the ESD violence prevention curriculum for TW. Further refinement and assessment of the feasibility and acceptability of the curriculum will occur in Phase 2 through the delivery of the tailored ESD curriculum to 3 groups of 16 TW. To assess the preliminary efficacy of the tailored intervention, program participants will complete a brief survey assessing the program directly after completion, as well as a battery of validated questionnaires assessing use of resistance strategies, gender-minority and general psychological factors hypothesized to mediate the behavioral effects of the intervention, and exposure to victimization experiences prior to, immediately following, and 6 months post-completion of the training.

#### **Research Design and Methodology**

The overall goal of this study is to use findings from Phase 1 (See protocol number 2020-0017) to deliver and refine a tailored ESD violence prevention training for diverse trans women. Participants for Phase 2 (n = 48) will be recruited from online forums including social media sites (e.g., Facebook, Twitter), banner ads on social networking/dating sites (e.g., Scruff, BGC Live, OK Cupid, Lex) that are trans-inclusive and through dissemination of paper and/or electronic recruitment flyers with leaders of community organizations that connect transgender individuals (e.g., AVP; Callen Lorde, Trans-lantinx network). Participants from prior studies who consented to future contact will be sent the study flyer by email. The proposed curriculum will be systematically refined based on delivery of the intervention to 3 groups of 16 TW each in a 20-hour training program, in 5 4-hour sessions. We have contracted with Prepare, Inc., the New York City chapter of IMPACT International to deliver the tailored ESD violence prevention intervention. IMPACT is an international ESD violence prevention organization with chapters across the United States. Prepare, Inc. will provide facilitators who have completed IMPACT's nationally standardized ESD violence prevention program requirements that include receipt of over 100 hours of training. IMPACT training is open to trans and cisgender women. The extensive training of IMPACT facilitators promotes intervention efficacy, while the risk of potential bias conferred by their experience with a pre-existing curriculum is mitigated by our community-engaged approach (i.e., TW community members, service providers, and scientists [PI and Co-I] collectively shape the content of the final tailored ESD intervention, and TW co-facilitators will be present in every training session). Prior to the start of group, facilitators will review the tailored curriculum in detail and attend 2-3 supervision/training meetings with the PI. These meetings will consist of reviewing the curriculum, role-plays of critical intervention components, and discussion of questions or concerns. The primary outcome of Aim 2 is to evaluate our ability to recruit our target (n = 48) and retain >75% over the course of the intervention. Successful completion of the pilot trial, including meeting or exceeding these benchmarks for success, will determine the feasibility and acceptability of recruiting participants into a future RCT. Preliminary efficacy of the tailored ESD violence prevention intervention will be evaluated as an exploratory aim. Participants enrolled in the pilot trial will be administered a battery of validated baseline questionnaires at baseline, immediately following the course, and 6 months after course completion (see Assessment Packet in attached below) including: - Demographics - Social Class Ladder- Community Ladder- Service Utilization Form - Sexual experiences Survey - Everyday Discrimination

Scale- Conflict Tactics Scale - Gender Minority Stress Risk and Resilience Scale - Post Traumatic Stress Disorder Symptom Checklist for DSM-5 (PCL-5)- Sexual Assertiveness Questionnaire- Resistance Tactics Survey- Dating Self-Protection - Illinois Rape Myth Acceptance - Resistance Self-Efficacy - Personal Progress- Transgender Congruence Scale - Depression Anxiety and Stress Scale - Quick Drinking Screen - DAST-10Brief acceptability checklists will be administered after each course session, which will contain a brief list of topics covered during that training session and participants will indicate which of the topics they felt were adequately covered (See page 38 of Assessment Packet, "Satisfaction and Fidelity Forms" for example items and formatting of this checklist). Lastly, an exit interview will be scheduled on the final day of the course, and will take place over the weeks immediately following the completion of the course. Interviews will be video recorded using the Zoom videoconferencing platform. The video-recorded qualitative interviews will be recorded and transcribed verbatim using the Zoom transcription function (omitting identifying information) and verified for accuracy. We will use three strategies to improve retention, based on an intensive evidence-based follow-up protocol with which the PI has considerable experience. First, participants will be compensated for completion of the assessment appointments at increasing increments over time (i.e., \$40 for baseline, \$30 for follow-up immediately after the course and \$30 for the exit interview after the course, \$80 for 6-month follow-up). Second, at baseline, participants will be asked to provide extensive locating information and to provide names of two local persons to be contacted in the event that the participant cannot be reached. This information will be updated at the time of follow-up survey administration. Third, participants will receive \$10 cash for each of the five session acceptability checklists they complete (one per session attended- up to \$50 total) which will be distributed at session 3/5 (up to \$30) and 5/5 (up to \$20). Analyses will be of two primary types: (a) examinations of whether feasibility targets were met across a variety of measures; and (b) examinations of the efficacy of the tailored ESD violence prevention intervention. We will use repeated measures one-way ANOVA to test if the tailored ESD curriculum has statistically significant effect on measures of behavioral and psychological/attitudinal change. If a significant effect is detected, we will use Tukey's pairwise-comparison procedure to compare all treatment means, with a 95% family confidence coefficient. To assess changes in exposure to victimization, we will collapse into three levels: (a) no history of victimization; (b) moderate victimization; (c) severe victimization. For this categorical data, a chi-square test of independence will be performed to compare posttreatment vs. pre-treatment, and 6-month FU vs. pre-treatment respectively to assess the preliminary efficacy of the program, with a family-wise type I error controlled at 0.05 using Bonferroni procedure. Our efficacy outcomes are exploratory and powered to detect large effect sizes. In the largest scale RCT of an ESD violence prevention program to date, rates of completed assault among women receiving resistance training were reduced by half at 1-year follow-up. However, as there are no existing studies that report on ESD efficacy among TW, we will use results of our exploratory efficacy analysis to shape power analyses for a subsequent, fully powered, RCT

Retrospective Data Review ONLY	No
Funding Requested/Obtained	Yes
Compensation for participation	Yes
Will participants incur any research related costs?	No
Is compensation available for research related injury?	No
Surveys or Questionnaires	Yes
Will the survey or questionnaire be self administered by the participants?	Yes
Do you intend to give feedback to participants based on survey/ questionnaire results?	No
Attach survey(s) / questionnaire(s)	
Title	ESD TW Phase 2 Assessment Packet (Survey Battery administration schedule on page 2, survey battery page 4-37)
Upload	Assessment packet_ESD for TW_10.12.20 (3).pdf

Interviews	Yes
Who will conduct the interview	[name], [name], [name], [name]
Will any individual(s) other than the research personnel be present during the interview?	No
Attach interview questions	
Title	ESD TW Phase 2 Assessment Packet (Interview on page 44)
Upload	Assessment packet_ESD for TW_10.12.20 (3).pdf
Observation	No
Audio or Video Recording or Photograph	Yes
Please be sure to insert templ consent document Check all that apply	ate language regarding recordings and/or photographs in the

Audio Recording

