List all research related procedures/data collection methods involving interaction or intervention with participants; use the Add New Procedure and Risk button to add each method. or intervention with

participants; use the Add New Procedure and Risk button to add each method.	
Procedure	Tailored IMPACT Basics Intervention
Where it will take place?	IMPACT Basics Course will take place at a well ventilated space centrally located and furnished by God's Love We Deliver ([name]).
When it will take place?	There will be three pilot series that will take place as part of this study. Series 1: 7/11/21, 7/18/21, 7/25/21, 8/1/21, 8/8/21Series 2: 9/19/21, 9/26/21, 10/3/21, 10/10/21, 10/17/21Series 3: 11/14/21, 11/21/21, 12/4/21, 12/11/21, 12/19/21As participants are recruited, they will be assigned to one of the three series based on their availability.
Frequency	As this study involves iterative tailoring of the intervention curriculum, the pilot intervention will be rolled out in 3 groups. Each pilot intervention will be followed by tailoring before rolling out the intervention to the following group. Thus, ESD violence prevention programming will take place 3 times, but each participant will only participate in one of the series.
Is procedure optional for participants?	Yes
Associated risk or discomfort	It is possible that participants may experience some discomfort while participating in the ESD violence prevention program.Due to the COVID-19 pandemic, in-person participation poses additional risk to participants.
Anticipated severity of risk or discomfort	No more than minimal risk
Expected frequency of risk or discomfort	The schedule for each of the 3 ESD series is outlined above. Participants will be assigned to one of the three series based on best availability match, so frequency of risk or discomfort is five times for five course sessions.

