Statistical Analysis Plan

"Empowerment Self-Defense Training for the Prevention of Victimization of Transgender Women" ID: R21MD014807 NCT04934189 1/18/2023

Statistical Design and Power

This R21 will use a non-experimental pilot study of 3 groups of 16 transgender women to assess preliminary feasibility and acceptability. A fully powered randomized controlled trial is neither practical nor advisable in this R21. The decision to use a single group, non-randomized design, rather than a randomized controlled trial (RCT), is best considered in light of critiques regarding the use of pilot RCTs to guide decision-making about whether to pursue larger-scale RCTs.⁷⁴⁻⁷⁶ The central point of these critiques is that because of their small size, pilot RCTs provide imprecise data on effect sizes, which can lead to both Type I and Type II errors. As a result, subsequent RCTs that are based on pilot RCTs may be underpowered (e.g., if pilot RCT suggests an artificially large effect size for the treatment [Type I error]) or not pursued (e.g., if pilot RCT suggests an artificially small effect size [Type II error]) even if the treatment could actually have been effective.⁷⁵ On the other hand, pilot trials do provide valuable information on the feasibility of study procedures, including recruitment, retention, implementation of the intervention, and data management. As the key objectives of this R21 are to develop the ESD self-defense training tailored for TW (Aim 1) and to assess its preliminary feasibility and acceptability (Aim 2), we will maximize the amount of useful information that can be gained about study feasibility and treatment efficacy in order to guide a future RCT of the new tailored violence prevention curriculum.

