Data Management. Following the CONSORT statement,⁸² we will track how many participants: (a) are told about the study; (b) are screened for the study; (c) do and do not meet inclusion criteria; (d) are invited to participate; and (e) actually enroll. Pre-inclusion attrition rates may reveal potential enrollment bias. To explore how differential refusal may affect generalizability of findings, we will also record the reasons for exclusion from and refusal to participate in the study. As recommended by the IOM Report,⁸³ we will model the effects of dropout patterns as data not missing at random using Bayesian analysis utilizing a pattern-mixture modeling approach. We will consider scale transformations, such as log, to decrease the effect of outliers.

Feasibility Analyses. The primary target outcomes of Aim 2 will be completion of the pilot study at the target recruitment total (n = 48), with < 25% dropout from assessments (Table 1. Research Plan). Secondary target outcomes related to assessment procedures, acceptability of the intervention, and laboratory and data management are detailed in Table 1 of the Research Plan. Successful completion of the pilot trial, including meeting or exceeding these benchmarks for success, will support the feasibility and acceptability of recruiting participants into a future RCT of the tailored ESD intervention using similar procedures and a similar population.

Power Analyses. Preliminary efficacy of the tailored ESD violence prevention intervention will be evaluated as an exploratory aim via administration of the battery of validated questionnaires assessing 1) behavior change variables (i.e., use of resistance tactics, self-protective behavior, and assertive relational communication); 2) psychological variables hypothesized to mediate the effects of the intervention on behavior (i.e., resistance self-efficacy, attributions of self-blame, rape myth acceptance, gender minority risk and resilience factors); and 3) reductions in rates of exposure to victimization) at baseline, post-intervention, and at the 3- and 6-month follow-up assessments.

Given its modest size and aims, this pilot is not powered to detect reductions in victimization exposure. Nonetheless, we will conduct exploratory analyses to evaluate potential trends that may emerge for the effects of treatment on behavior change, violence risk and resilience variables, and victimization.

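### Meeting the recruitment and retention benchmarks cannot settle whether women can be recruited into a randomized trial: the course is guaranteed to all, and the retention threshold has no interval

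*Protocol*

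**What the plan says.** Protocol section 5 (Research Design and Methodology) gives the primary outcome of Aim 2 as the ability to "recruit our target (n = 48) and retain >75% over the course of the intervention". It then says that successful completion, including meeting these benchmarks, "will determine the feasibility and acceptability of recruiting participants into a future RCT".

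The SAP (Feasibility Analyses) keeps the target of 48 but words the second benchmark as completion "with < 25% dropout from assessments". Its conclusion is softer: a pass "will support the feasibility and acceptability of recruiting participants into a future RCT of the tailored ESD intervention using similar procedures and a similar population".

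The design is a "non-experimental pilot study of 3 groups of 16 transgender women" (SAP, Statistical Design and Power). On placement, Protocol section 6 says that as women are recruited "they will be assigned to one of the three series based on their availability". All three series deliver the course.

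The analysis text says only that the plan will examine whether feasibility targets were met. Neither document attaches a confidence interval, a test or an error rate to the benchmark.

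**The concern.** The conclusion concerns recruitment into a randomized trial, but the study observes recruitment into an open course. A woman who joins knows that she will be offered the training. In a randomized trial she would have to accept that chance decides, and some women would have to stay in follow-up under the comparison condition. Neither step occurs here. The SAP's condition of similar procedures does not close the gap, because allocation is the procedure that would differ.

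The plan's own retention strategy shows why carry-over cannot be assumed. One of its three elements is $10 cash for each session checklist, up to $50, which a comparison arm without sessions would not receive.

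Separately, reading retention as met or not met from 48 women gives a verdict without its uncertainty. This is the primary outcome of Aim 2 and is meant to guide planning of the next trial. A pass could be taken as evidence on two things it does not establish: that randomization is acceptable, and that true retention exceeds 75%.

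**Working it through.** **1. What is observed and what is concluded**

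| Needed for the conclusion | What the plan provides |
|---|---|
| Uptake when allocation is by chance | Uptake of a guaranteed course; placement by availability |
| Retention in a comparison condition | Retention of women who are all offered the course |
| Reasons for declining randomization | Reasons for exclusion and refusal (SAP, Data Management), for an open course |

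The documents give no rate of acceptance of randomization, so the gap cannot be estimated. As an assumption only: if 50% to 90% of the same 48 volunteers would accept it, 48 × 0.5 = 24 to 48 × 0.9 ≈ 43 could be randomized.

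**2. The plan's own figures**

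- Sample: 3 × 16 = 48, which reproduces.
- Protocol benchmark: 0.75 × 48 = 36 is exactly 75%, so more than 75% means at least 37.
- SAP benchmark: 0.25 × 48 = 12, so less than 25% dropout means at most 11 lost, again at least 37 kept. The count is the same, but the event counted is not.
- The SAP's sample-size tables reproduce in every cell (noncentral t with d = ES/8, one-sided 0.05; noncentral chi-square with 2 df, 0.05). They concern efficacy and do not justify the 48 or the 75% as feasibility targets.

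**3. Precision of the lowest pass**

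Estimate: 37/48 = 77.1%. Clopper-Pearson 95% limits:

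- lower = 2.5% quantile of Beta(37, 12) = 62.7%
- upper = 97.5% quantile of Beta(38, 11) = 88.0%

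**4. How often the rule is met**

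P(X ≥ 37) = Σ C(48, k) pᵏ (1 − p)⁴⁸⁻ᵏ, summed over k = 37 to 48.

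| True retention p | Probability of meeting the benchmark |
|---|---|
| 65% | 0.05 |
| 70% | 0.18 |
| 75% | 0.44 |
| 80% | 0.76 |
| 85% | 0.95 |

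A study whose true retention is only 75% passes 44% of the time. One with true retention of 80% fails 1 − 0.76 = 24% of the time.

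**5. What would show retention above 75%**

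The documents state no error rate, so one-sided 0.05 is an assumption. The smallest count r with P(X ≥ r | p = 0.75) ≤ 0.05 is 42/48 (87.5%), where the probability is 0.027. That count is reached with probability 0.41 at true retention of 85% and 0.80 at 90%.

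**6. Sensitivity**

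- Clustering: the figures above treat women as independent. With design effect 1 + (16 − 1) × ICC and an assumed ICC of 0.05, this is 1.75. The approximate 95% half-width at 75% rises from 1.96 × √(0.75 × 0.25/48) = 12 points to 1.96 × √(0.75 × 0.25/27.4) = 16 points. An ICC of 0.02 gives 14 points and 0.10 gives 19 points.
- Denominator: Protocol section 10 sets an enrollment ceiling of 80. On that base, 0.75 × 80 = 60, so the rule needs at least 61, and it is met with probability 0.14 at true retention of 70%.

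**The case against.** The strongest reply is that the single-arm design is deliberate. The SAP argues that small pilot RCTs give imprecise effect sizes, and it lists recruitment, retention, implementation and data management as what a pilot can inform. Aim 2 does not claim to test randomization. This stands: a reader might infer that the pilot should have been randomized, and the documents do not support that. The defect is the conclusion drawn, not the design.

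Other parts of the reply also stand:

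- The SAP already uses the softer verb and limits itself to similar procedures and a similar population. What remains is its reference to randomized recruitment and its mismatch with the protocol.
- A reader might infer that everything rests on one proportion or on a formal stop/go rule. It does not. There are two primary benchmarks, secondary targets, flow counts, session checklists and exit interviews, and no automatic progression rule is stated.
- A reader might infer that willingness to be randomized is never asked. That cannot be verified. The Assessment Packet (with the interview guide), the screener and Table 1 of the Research Plan are not supplied. A question there would still not be an offer of randomization.
- A reader might infer that the pilot would pass while a control arm would fail. The documents give no control-arm retention and name no comparator. Depending on what is assumed, the table above gives anything from 0.05 to 0.95, and at equal retention the contrast disappears. Assessment payments and locator contacts need not depend on receiving the course.

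The missing interval can be calculated later from reported counts, so it is a reporting gap rather than a design fault. It still matters if the result is read as pass or fail.

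**Conclusion.** The point holds in a limited form. Meeting the benchmarks can support the feasibility of recruitment and retention when the course is guaranteed. It cannot determine the feasibility or acceptability of recruiting into a randomized trial, because no participant is asked to accept chance allocation or a comparison condition.

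Nor does a pass establish true retention above 75%: the lowest passing result is compatible with about 63%. This rests on a base of 48 and independent women; clustering within the three groups would widen the interval. It needs no assumption about a control arm.

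The retention definition is also unsettled. The protocol counts retention over the intervention and the SAP counts dropout from assessments. The SAP further lists a 3-month follow-up that the protocol's three-survey schedule lacks, so the assessments that count need to be named.

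The conclusion is overstated and should be corrected, but the correction is small.

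**What to change.** 1. **Wording.** Align the protocol with the SAP and limit both to this: meeting the benchmarks *will support the feasibility of recruitment and retention when the course is guaranteed*.
2. **Retention.** State one definition (which event, which assessments, which denominator) and report the proportion with an exact 95% CI.
3. **Recruitment.** Report the flow counts that the SAP already plans to collect, with the uptake proportion.
4. **Randomization.** If contacts remain, add one item on willingness to join under chance allocation. Ask participants at a survey or the exit interview. Ask decliners inside the screener, because screening collects no identifying information and they could not be followed up. Otherwise, state as a limitation that acceptability of randomization was not tested.

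Items 1 to 3 cost a few sentences and one interval and can be done at reporting. Item 4 may come too late: the planned sessions end on 12/19/21, six-month follow-up would fall around June 2022, and the SAP is dated 1/18/2023. The downsides are a narrower conclusion and, if the item is asked, that a hypothetical answer is an imperfect proxy for real consent to randomization.

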A power analysis was performed using the R package WebPower for a representative variable for each these three outcomes categories. Sample size can be derived based on effect size (f) and power (1- β). Here f= σ_m/σ , Cohen (1988, p. 275), σ_m is the standard deviation of population means and σ the standard deviation within the populations. Even though Cohen (1988) provides general magnitudes for small effect size: f = 0.1, medium effect size: f = 0.25, large effect size: f = 0.5, he argues that these guidelines are to be used when there is insufficient prior knowledge and "may not be reasonably descriptive in any specific area." The preliminary efficacy results derived from the proposed pilot trial will further inform our estimate of an effect size

of clinical interest for these outcomes. This information will be used to plan for a sufficiently powered confirmatory trial (e.g., R01).

1. Behavior Change Variable: use of self-protective behavior

Test procedure: paired two-sample t-test, one-sided, $\alpha = 0.05$, $s_d = 8$

Power calculation: GPower

	Power				
Effect Size (ES)	0.8	0.85	0.9	0.95	
1	398	462	550	694	
1.5	178	206	245	310	
2	101	117	139	175	
2.5	65	75	90	113	
3	46	53	63	79	

2. Attitudinal Mediator Variable: self-efficacy

Test procedure: paired two-sample t-test, one-sided, $\alpha = 0.05$, $s_d = 8$

Power calculation: GPower

	Power				
Effect Size (ES)	0.8	0.85	0.9	0.95	
1	398	462	550	694	
1.5	178	206	245	310	
2	101	117	139	175	
2.5	65	75	90	113	
3	46	53	63	79	

3. Reductions in Exposure to Victimization Variable: sexual victimization reduction

Test procedure: chi-square test for independence, two-sided, df = 2, α = 0.05

Power calculation: R package powerAnalysis

	Power				
Effect Size (ES)	0.8	0.85	0.9	0.95	
0.1	964	1093	1266	1545	
0.2	241	274	317	387	
0.3	108	122	141	172	
0.4	61	69	80	97	
0.5	39	44	51	62	

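### The protocol's power claim covers victimization although the SAP disclaims power for it, and the SAP's victimization sample sizes use alpha 0.05 instead of the planned Bonferroni level

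*Protocol*

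**What the plan says.** Protocol, section 5, Research Design and Methodology, describes chi-square tests of a three-level victimization variable: post-treatment against pre-treatment, and 6-month follow-up against pre-treatment, with Bonferroni control at 0.05. The next sentence reads "Our efficacy outcomes are exploratory and powered to detect large effect sizes". It covers the efficacy outcomes as a group. The protocol then cites an earlier randomized trial in which "rates of completed assault among women receiving resistance training were reduced by half at 1-year follow-up".

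The SAP, under Power Analyses, says "this pilot is not powered to detect reductions in victimization exposure" and promises only an exploratory look for trends. It nevertheless gives a sample-size table for sexual victimization, with the test specified as "chi-square test for independence, two-sided, df = 2, α = 0.05". The smallest N in that table is 39, at effect size 0.5 and 80% power. Under Inferential analyses the SAP plans three victimization contrasts, adding a 3-month follow-up that the protocol's schedule does not contain, again with Bonferroni control.

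The target sample is 48 women in one group, "with < 25% dropout from assessments".

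**The concern.** Two things do not fit together.

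First, a reader of the protocol alone is told that victimization, like the other efficacy outcomes, is powered for large effects. A reader of the SAP is told that it is not powered. Neither document states a condition that would make both true. The SAP's own table, with 39 below the planned 48, sits more easily with the protocol's sentence than with the SAP's.

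Second, the victimization table is computed at an alpha that the planned test will not use, so its sample sizes are too small for that test.

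What is at stake is how a non-significant victimization result is read. The protocol says the exploratory results will shape the power analysis of a later randomized trial. Someone relying on the protocol's sentence could take a null result as evidence against a large effect, when the information in the data may be too thin for that.

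**Working it through.** **Inputs from the documents.** 48 women; dropout limit 25%, so 48 × 0.75 = 36 women. Two waves per contrast, so 96 records, or 72 at the dropout limit. A 2 × 3 table, df = 2. Bonferroni alpha 0.05/2 = 0.025 (protocol) or 0.05/3 = 0.0167 (SAP).

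**Assumed.** Baseline victimization rate, which neither document gives. Shown at 40%, 50%, 60% and 80%.

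**Formula.** Power is the probability that a noncentral chi-square with df = 2 and noncentrality λ = N·w² exceeds the critical value. With df = 2 the critical value is −2 ln(alpha): 5.991 at 0.05, 7.378 at 0.025, 8.189 at 0.0167.

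**Step 1: reproduce the SAP table.** At alpha 0.05, 80% power needs λ = 9.635. At w = 0.5, N = 9.635/0.25 = 38.5, so 39, as printed. All 20 entries reproduce exactly, which shows that the table's effect size is Cohen's w and that no multiplicity adjustment was made.

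**Step 2: apply the planned alpha.** For 80% power at w = 0.5:

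- alpha 0.025: λ = 11.493, N = 11.493/0.25 = 45.97, so 46
- alpha 0.0167: λ = 12.558, N = 12.558/0.25 = 50.2, so 51

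**Step 3: what N counts.** The formula takes N as total observations, but the table does not say whether a reader should compare it with women or with records. Power at w = 0.5:

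| N | alpha 0.05 | 0.025 | 0.0167 |
|---|---|---|---|
| 36 women | 77% | 68% | 62% |
| 48 women | 88% | 82% | 78% |
| 72 records | 97% | 95% | 94% |
| 96 records | 99.5% | 99% | 98.5% |

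Counted as women, 48 clears 80% with two contrasts and just misses it with three; 36 misses at every alpha. Counted as records, there is no shortfall at 0.5.

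**Step 4: a halving, on the plan's own test.** For a rate falling from p to p/2, equal numbers at the two waves and an unchanged moderate-to-severe ratio, w = (p/4)/√[0.75p(1 − 0.75p)]. At p = 50%: 0.125/√(0.375 × 0.625) = 0.26.

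| Baseline | w | Power, 96 records: 0.025 | 0.0167 | Power, 72 records: 0.025 | 0.0167 |
|---|---|---|---|---|---|
| 40% | 0.22 | 36% | 30% | 26% | 22% |
| 50% | 0.26 | 50% | 44% | 38% | 32% |
| 60% | 0.30 | 66% | 61% | 51% | 45% |
| 80% | 0.41 | 92% | 90% | 82% | 78% |

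Setting w = 0.5 gives p = 0.1875/0.203125 = 92.3%, so a halving matches the table's largest effect only from a baseline of about 92%.

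These figures treat the two waves as independent samples, as the planned test does, although the same women contribute to both. I have not computed power for a paired test.

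**The case against.** The case for leaving this alone is fair in several respects. The protocol's sentence itself calls the outcomes exploratory. The SAP disclaims power for victimization and, under Statistical Design and Power, explains that small pilot trials give imprecise effect sizes that can wrongly end a line of research. The success criteria are recruitment and retention; no decision to proceed rests on victimization. The two power statements are also logically compatible if realistic reductions are smaller than large ones. The table contains no arithmetic error at its stated alpha, and on a records count it supports detection of an effect of 0.5 even after Bonferroni.

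These points limit the seriousness. They do not supply the missing condition that would reconcile the two statements, and they do not touch the alpha mismatch, which needs no assumed baseline.

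Some stronger readings are tempting but unsupported:

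- A reader might infer that the design would usually miss a halving. That depends on a baseline rate the documents do not give. With 96 records power is at least 90% at an 80% baseline.
- A reader might take the halving as the effect this pilot aims at. The protocol cites it as prior evidence and goes on to say that no efficacy studies exist in this population.
- A reader might say that a halving is not large by the SAP's own scale. The SAP's label is "large effect size: f = 0.5", a measure for comparing means; no row of the victimization table is labelled.

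**Conclusion.** The point holds as an inconsistency in wording together with an alpha mismatch. The protocol claims power for large effects without exempting victimization, and the SAP disclaims it. The SAP's victimization sample sizes are too small for the Bonferroni-adjusted test: 39 should be 46 or 51, depending on whether two or three contrasts are planned. The consequence at effect size 0.5 ranges from none (N as records) to power of 62% to 68% (N as women, at the dropout limit).

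That a null victimization result could be misread is a risk at low to moderate baselines, where power for a halving with all 48 women followed is between 30% and 66% over assumed baselines of 40% to 60%. It would be too strong to say that such a result will be misread, since both documents call efficacy exploratory.

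The halving figures rest on the assumed baseline, proportional reduction in moderate and severe victimization, and independence between waves. Severity is minor to moderate: the outcome is exploratory and the feasibility aims are unaffected.

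**What to change.** - In the protocol, limit the power sentence to the behavioral and psychological outcomes, and add the SAP's statement that the pilot is not powered for reductions in victimization.
- In the SAP, settle whether there are two or three victimization contrasts, since the protocol has no 3-month assessment, and recompute the third power table at the resulting alpha.
- State in that table that the effect size is Cohen's w, and whether N counts women or records.
- Report change in victimization as an estimate with a confidence interval, and say that a non-significant result is not evidence of no effect.

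The cost is a few sentences across the two documents and one recomputed table of 20 entries. No change to sample size or data collection is needed for this point. The drawback is that the stated power becomes less favorable.
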